**10.4 Performance Status**

Patients will be graded according to the Zubrod Performance Status Scale.

POINT	DESCRIPTION
0	Fully active, able to carry on all pre-disease performance without restriction.
1	Restricted in physically strenuous activity but ambulatory and able to carry out work of a light or sedentary nature, e.g., light housework, office work.
2	Ambulatory and capable of self-care but unable to carry out any work activities; up and about more than 50% of waking hours.
3	Capable of limited self-care, confined to bed or chair more than 50% of waking hours.
4	Completely disabled; cannot carry on any self-care; totally confined to bed or chair.

**10.5 Time to Death**

From date of sub-study registration to date of death due to any cause. Patients last known to be alive are censored at date of last contact.

**10.6 Investigator-Assessed Progression-Free Survival**

From date of sub-study registration to date of first documentation of progression assessed by local review or symptomatic deterioration (as defined above), or death due to any cause. Patients last known to be alive without report of progression are censored at date of last disease assessment. For patients with a missing scan (or consecutive missing scans) whose subsequent scan determines progression, the expected date of the first missing scan (as defined by the disease assessment schedule) will be used as the date of progression.

**10.7 Progression-Free Survival by Central Review**

From date of sub-study registration to date of first documentation of progression assessed by central review or symptomatic deterioration (as defined above), or death due to any cause. Patients last known to be alive without report of progression are censored at date of last disease assessment. For patients with a missing scan (or consecutive missing scans) whose subsequent scan determines progression, the expected date of the first missing scan (as defined by the disease assessment schedule) will be used as the date of progression.

**10.8 Duration of Response (DoR)**

From date of first documentation of response (CR or PR) to date of first documentation of progression assessed by local review or symptomatic deterioration (as defined above), or death due to any cause among patients who achieve a response (CR or PR). Patients last known to be alive without report of progression are censored at date of last disease assessment. For patients with a missing scan (or consecutive missing scans) whose subsequent scan determines progression, the expected date of the first missing scan (as defined by the disease assessment schedule) will be used as the date of progression.

## 11.0 STATISTICAL CONSIDERATIONS

### 11.1 Sample Size with Power Justification

The primary objective is to evaluate the response rate for rucaparib among patients found to have LOH or BRCA positive tumors as summarized in Table 1.

**Table 1. Eligibility Biomarkers**

Biomarker-positive group	Alteration type	Eligible alteration
LOH	Loss of Heterozygosity (LOH)	Genomic LOH $\geq 21\%$
BRCA	Homologous Recombination Deficiency (HRD)	Deleterious mutation in BRCA1 or BRCA2

This study will use the Phase II design implemented in biomarker-driven sub-studies within Lung-MAP. The study will evaluate rucaparib among patients with tumors defined to meet the biomarker eligibility criteria defined in Table 1.

Accrual will be stratified into the cohorts by histology as defined in [Section 6.0](#) (squamous and non-squamous histology). The following details pertain to each cohort.

Within a cohort, the accrual goal is 40 eligible and evaluable patients. Patients will be considered evaluable if they receive at least one dose of rucaparib. Assuming that 10% of patients who are enrolled will be not eligible or evaluable retrospectively, the total accrual goal per cohort is 44 patients, for a total of 88 patients in the study.

A design with 91% power and 1-sided 0.05 level type I error would require 40 patients/cohort to rule out an objective response rate (ORR) of 15% or less if the true ORR is 35% or greater. Calculations were performed using the calculators at [www.swogstat.org](http://www.swogstat.org). We note that the exact power and type I error are 93% and 6.6%, respectively.

The expected prevalence of LOH positivity is 16% for Cohort 1 (squamous) and 9% for Cohort 2 (non-squamous). The expected prevalence of BRCA 1/2 is 5.8% for squamous patients and 1.4% for non-squamous patients. The estimated percentage of patients with both LOH+ and BRCA+ cancers is 0.1% for cohort 1 and 1% for cohort 2 resulting in an estimate eligibility rate for the study of 22% for squamous histology NSCLC and 11% for non-squamous NSCLC.

Sites are notified of a patient's sub-study assignment by the SWOG Statistics and Data Management Center (SDMC) after the results of the biomarker testing have been reported to the SDMC. As described in [LUNGMAP](#) Section 11.0 (the Lung-MAP screening protocol), patients with biomarkers matching only this study will be assigned to this study and sub-study assignment will be based on randomization for patients eligible for multiple biomarker-driven sub-studies. The frequency of patients assigned to this sub-study will

depend on the other biomarker-driven sub-studies actively accruing while this study is accruing and could be less than the percentages eligible for the sub-studies. To account for this, the estimated percentage of screened patients (with successful biomarker testing) assigned to this study is 20% (same for both cohorts).

The expected average monthly accrual rate is 4 patients/cohort per month. We expect the rates to be approximately equal between the cohorts given the history of Lung-MAP focusing on squamous and abundance of competing studies in non-squamous histology, despite the fact that prevalence of squamous histology is about a quarter of all NSCLC. The anticipated duration of accrual is 11 months per cohort.

## 11.2 Analysis Plan

An interim analysis will take place when 20 patients/cohort are evaluable for response. Evaluability for response is defined based on RECIST 1.1 and accrual is to remain open while patients are being evaluated for response. However, if 20 or more eligible patients/cohort for the first interim analysis have made it to their second disease assessment and the required number of responses to continue past that interim analysis has not been observed, then the accrual to the cohort will be placed in temporary closure until the response status for all patients in the interim analysis set is known.

This interim analysis will only evaluate early stopping for futility. If 2 or fewer responses are observed (within a cohort), this will be considered evidence of futility and the recommendation will be to close the cohort for lack of evidence of efficacy of the regimen. Interim decisions within a cohort will not affect the outcome of the other cohort.

**If the study continues to full accrual, the observation of at least 10 responses within a cohort will be considered evidence to rule out the null hypothesis of a 15% response rate within that cohort.**

Response rates and associated confidence intervals will be calculated. OS, IA-PFS, and DoR will be estimated using the method of Kaplan-Meier. The Brookmeyer-Crowley method will be used to calculate confidence intervals for median times. With 40 patients, response rates can be estimated within 16% with 95% confidence.

Toxicity will be evaluated among all patients enrolled on the study (combining the squamous and non-squamous cohorts). With 80 patients, any toxicity can be estimated to within 11% with 95% confidence. Any toxicity with at least 5% prevalence has at least a 98% chance of being observed.

Analysis of IA-PFS will take place when 31 IA-PFS events/cohort have been observed. A key secondary objective is an assessment of median IA-PFS (mPFS). If the ORR rate is less than 25%, but the mPFS is at least 4.5 months, this may be considered sufficient evidence to continue to the follow-on Phase III. With 40 patients/cohort this design has 87% power to rule out a mPFS of 3 months or less, if the true mPFS is 6 months, at the 0.05 1-sided level. This is based on using Brookmeyer-Crowley test of null of 3 month mPFS versus alternative of 6 month mPFS with 10 months of accrual and 6 months' follow-up. The observation of an mPFS of at least 4.6 months would be considered evidence to rule out an mPFS of 3 months or less.

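### The 10-response success cutoff is calibrated to 40 evaluable patients per cohort, but 44 are registered and Section 11 gives no rule for any other attained number

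*Combined protocol and SAP*

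**What the plan says.** Section 11.1 sets the design number: "Within a cohort, the accrual goal is 40 eligible and evaluable patients". It defines the term broadly: "Patients will be considered evaluable if they receive at least one dose of rucaparib". It then adds an allowance for losses: "Assuming that 10% of patients who are enrolled will be not eligible or evaluable retrospectively, the total accrual goal per cohort is 44 patients". After the nominal design (15% against 35%, one-sided 0.05, 91% power) it reports the exact properties: "We note that the exact power and type I error are 93% and 6.6%, respectively".

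Section 11.2 puts a futility look at 20 patients per cohort, stopping at 2 or fewer responses. The final rule opens with "If the study continues to full accrual" and continues that "the observation of at least 10 responses within a cohort will be considered evidence to rule out the null hypothesis" of 15%. No denominator is given.

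The PFS paragraph of Section 11.2 adds a second route: "If the ORR rate is less than 25%, but the mPFS is at least 4.5 months", then "this may be considered sufficient evidence to continue to the follow-on Phase III". The 25% there equals 10/40.

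**The concern.** A fixed count of responses has a given error rate only for a given number of patients. Ineligibility and non-treatment are settled after enrolment, and one dose is enough to be evaluable, so a cohort that registers 44 can end with anything up to 44 in the analysis. Above 40, ten responses are easier to reach by chance under a true rate of 15%, and the disclosed 6.6% no longer describes the test. Below 40, the error falls and so does power.

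The plan also does not say whether the test uses 40 patients or everyone evaluable. If a cohort ends with 43 evaluable patients and the tenth responder is the 42nd registered, the verdict depends on a choice that nobody has written down and that could be made with the responses known. Section 2.2 makes reaching the required number of responses the signal for randomized trials, so this is the main decision in each cohort.

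**Working it through.** **Inputs.** From Section 11.1: 40 evaluable and 44 registered per cohort, 10% loss, null response rate 0.15, alternative 0.35. From Section 11.2: futility look at 20, stop at 2 or fewer responses; success at 10 or more.

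**Formula.** For a final number n and cutoff r, with the first 20 patients forming the interim set,

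P(success; p) = Σ over x = 3,…,20 of Bin(x; 20, p) × P[Bin(n − 20, p) ≥ r − x].

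Type I error is the value at p = 0.15, and power the value at p = 0.35.

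**Reproducing the plan.** For n = 40 and r = 10 this gives 6.57% and 93.1%, which match the disclosed 6.6% and 93%. Without the futility look the figures would be 6.72% and 93.6%, so the disclosed error includes the look.

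**Other attained numbers, futility look included.**

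| n | Type I error, r = 10 | Power, r = 10 | Type I error, r = 11 | Power, r = 11 |
|---|---|---|---|---|
| 35 | 2.9% | 83.4% | | |
| 36 | 3.5% | 86.0% | | |
| 37 | 4.1% | 88.2% | | |
| 38 | 4.9% | 90.1% | | |
| 39 | 5.7% | 91.8% | | |
| 40 | 6.6% | 93.1% | 3.0% | 87.6% |
| 41 | 7.5% | 94.2% | 3.5% | 89.5% |
| 42 | 8.6% | 95.2% | 4.1% | 91.2% |
| 43 | 9.7% | 95.9% | 4.8% | 92.6% |
| 44 | 10.8% | 96.5% | 5.5% | 93.7% |

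**How likely each case is.** The plan gives only the 10%. As an assumption, let each of the 44 be evaluable independently with probability 0.9, so that 44 × 0.9 = 39.6 are expected. Then:

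- P(n > 40) = 34.7%, P(n = 40) = 20.1%, P(n < 40) = 45.3%, P(n = 44) = 1.0%.
- At least one of two independent cohorts above 40: 1 − (1 − 0.3466)² = 57%.
- The result is sensitive to the loss rate: P(n > 40) is 21% at 12% loss, 53% at 8% and 82% at 5%.

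**Averages with the cutoff fixed at 10, all evaluable patients counted.**

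- Given n > 40: type I error 8.2%, power 94.8%.
- Given n < 40: type I error 4.8%, power 89.6%.
- Over all n: type I error 6.35%, power 92.1%.

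**The 25% in the PFS paragraph.** Ten responses are 24.4% of 41 and 22.7% of 44. A cohort there has met the response cutoff and also falls under the branch for a rate below 25%. Under the same loss model, exactly 10 responses with n = 41–44 has probability 1.5%, 4.7% and 1.5% at true rates of 15%, 25% and 35%.

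**The case against.** The arithmetic and the missing denominator are not in dispute. The case against rests on how much they matter.

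- **No inflation on average.** At the plan's own loss rate the average error is 6.35%, below the disclosed 6.6%, and ending under 40 (45.3%) is more likely than ending over it (34.7%). This stands. It limits the size of the point but does not settle which patients count, and a cohort is judged at the number it reaches.
- **The verdict rarely changes.** Testing all evaluable patients and testing the first 40 give different answers with probability 0.6%, 1.9% and 0.6% per cohort at true rates of 15%, 25% and 35%. This also stands.
- **The text can be read as meaning 40.** Section 11.1 calls 40 the goal for evaluable patients, and the precision statement in Section 11.2 uses 40. But Section 11.1 also gives 44 as the total accrual goal, and the success rule applies at full accrual, so the reading is not secured.
- **The screening protocol may contain a rule.** Sections 2.1 and 11.1 refer to the wider Lung-MAP design. That document was not available, so the point concerns Section 11 as written.
- **The interim set may not be exactly the first 20.** Interim evaluability follows RECIST 1.1 and final evaluability follows dosing, so the two sets need not nest. Looks at 18 to 24 patients move the error only to 7.3–7.7% at n = 41 and 10.3–11.2% at n = 44.
- **The 25% branch is permissive.** A cohort that has met the cutoff needs no second route. This is an overlap, not a contradiction.

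**Conclusion.** The concern holds and should be fixed. The disclosed 6.6% and 93% belong to one attained number, 40, which has about a 20% chance under binomial loss at 10%. With the stated cutoff, the type I error exceeds 6.6% at every number from 41 to 44. The 10.8% at 44 is an upper bound with about 1% probability; 8.2% is the average when more than 40 are evaluable. The conclusion that the error exceeds 6.6% above 40 does not depend on the loss model. The probabilities and averages do, and they also assume an interim at exactly 20 patients who are part of the final set.

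**What to change.** State in Section 11.2 that the primary test in each cohort uses the first 40 eligible patients, in order of registration, who received at least one dose; that this set is fixed by eligibility and treatment review without regard to response; and that success is 10 or more responses among them. With fewer than 40, keep the cutoff at 10 (type I error 2.9–5.7% and power 83–92% for n = 35–39). Also report the response rate and confidence interval in all eligible, treated patients. This retains 6.6% and 93% whenever at least 40 are evaluable, given the interim at 20 as planned.

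**Cost.** Wording only, with no extra patients. Averaged over 10% binomial loss, power moves from 92.1% to 91.5% and type I error from 6.35% to 5.8%. Given more than 40 evaluable, power is 93.1% instead of 94.8%. Up to 4 treated patients per cohort stay outside the primary test.

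**Alternative.** If every evaluable patient is to be tested, give the cutoff by attained number: at least 10 for n = 35–40 and at least 11 for n = 41–44. Type I error at 41–44 is then 3.5–5.5%, with power 89.5–93.7%. Average type I error falls to about 4.9% and average power to about 90.7%, some 1.4 points below the current rule, and power drops from 93.1% at 40 patients to 89.5% at 41. The first-40 rule is simpler.

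In either case, make the PFS branch conditional on the primary response cutoff not being met, in place of the 25% figure, so that the two rules agree at any n. If the screening protocol already contains a rule for attained numbers, cite it in Section 11.2 and give the error rates that follow from it.

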### 1.2 Secondary Objectives

- a. To evaluate investigator assessed progression-free survival (IA-PFS) and overall survival (OS) associated with rucaparib within each cohort.
- b. To evaluate duration of response among responders within each cohort.
- c. To evaluate the frequency and severity of toxicities associated with rucaparib among all patients enrolled on the study (combining cohorts).

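### The toxicity population is everyone enrolled, so rates would be diluted, modestly, if any registered patient never takes rucaparib

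*Combined protocol and SAP*

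**What the plan says.** The toxicity population appears in two places, with matching wording.

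- Section 1.2, objective c: "To evaluate the frequency and severity of toxicities associated with rucaparib among all patients enrolled on the study (combining cohorts").
- Section 11.2, Analysis Plan: "Toxicity will be evaluated among all patients enrolled on the study (combining the squamous and non-squamous cohorts").

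Section 11.2 then gives two planning figures for toxicity: "With 80 patients, any toxicity can be estimated to within 11% with 95% confidence" and "Any toxicity with at least 5% prevalence has at least a 98% chance of being observed".

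Section 11.1 sets the numbers behind these. "Within a cohort, the accrual goal is 40 eligible and evaluable patients", and "Patients will be considered evaluable if they receive at least one dose of rucaparib". The enrolment target is raised to 44 per cohort, 88 in all, on this basis: "Assuming that 10% of patients who are enrolled will be not eligible or evaluable retrospectively". Ineligible and undosed patients are pooled in that 10%.

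Section 14.1 requires data on every registered patient, including those who are not given the assigned treatment. Section 11 does not define a treated-patient safety set.

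**The concern.** Objective 1.2c is about toxicities attributable to rucaparib. A patient who registers but never takes the drug cannot have one, so keeping that patient in the denominator can only lower the reported rate.

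The plan makes room for such patients. Evaluability requires a dose, the 10% allowance includes patients who are not evaluable, and Section 14.1 collects data on untreated registrants. Registration also comes before dosing: Section 13.1 asks only that patients plan to start within 10 days of registering.

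Elsewhere the protocol does tie safety to exposure, since expedited reporting in Section 16.1e applies once a patient has had a dose. The toxicity analysis population carries no such condition.

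At stake is the accuracy of a secondary safety endpoint in a trial that Section 16.0 (Trial Master File) calls a potential registration study. Any error from this source would make the drug look slightly better tolerated than it is.

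**Working it through.** **Inputs**

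- Planned enrolment: 44 × 2 = 88 (Section 11.1).
- Planned eligible and dosed patients: 40 × 2 = 80 (Section 11.1).
- Allowance for ineligible or non-evaluable patients: 88 − 80 = 8 (Section 11.1).
- Number never dosed: not stated. Assumed range 0 to 8.

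**Step 1. The plan's own figures.** The worst-case 95% half-width is 1.96 × √(0.25/n). The chance of seeing at least one case of a 5% toxicity is 1 − 0.95^n.

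| n | Half-width | Chance of at least one case |
|---|---|---|
| 80 | 1.96 × √(0.25/80) = 10.96 points | 1 − 0.95^80 = 98.3% |
| 88 | 1.96 × √(0.25/88) = 10.45 points | 1 − 0.95^88 = 98.9% |

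The stated 11% and 98% reproduce at 80. Because they are worded as bounds, they also hold at 88. They therefore contain no error, and they do not settle which population is meant.

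**Step 2. Dilution.** If the true rate among dosed patients is p, the rate over all enrolled is p × (dosed/enrolled).

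| Undosed of 88 | Factor | True 5% reads | True 20% reads | True 40% reads | True 50% reads |
|---|---|---|---|---|---|
| 0 | 88/88 = 1.000 | 5.0% | 20.0% | 40.0% | 50.0% |
| 2 | 86/88 = 0.977 | 4.9% | 19.5% | 39.1% | 48.9% |
| 4 | 84/88 = 0.955 | 4.8% | 19.1% | 38.2% | 47.7% |
| 8 | 80/88 = 0.909 | 4.5% | 18.2% | 36.4% | 45.5% |

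The last row is the limiting case under the plan's allowance: a relative shrinkage of 8/88 = 9.1%, or 0.5 points at a true 5% and 4.5 points at a true 50%. It requires that all 8 losses be undosed and none be dosed but ineligible.

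**Step 3. Wording against number.** The text gives the population as everyone enrolled, planned at 88. The precision sentence uses 80, which equals the planned number who are both eligible and dosed. Neither describes all dosed patients: the first can include undosed patients, and the second leaves out patients who were dosed but later found ineligible. If accrual goals are met, the dosed set would number at least 80 and at most 88.

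**The case against.** The strongest reply is that no bias is established. Dilution needs some patients to be undosed and also to be kept in the denominator. The documents give no count of undosed patients, and with none the effect is exactly zero. The 10% allowance also covers ineligible patients, and Section 14.1 says that patients with inadequate documentation will usually be classed as ineligible; such patients may well have been dosed. All of this stands. A reader might infer that the plan understates rucaparib toxicity, or that every reported frequency is biased downward. The documents do not support either statement as a fact; they support only the conditional one.

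A second reply is that the phrase about all enrolled patients may simply mean pooled cohorts, in contrast with the efficacy objectives, which are set within each cohort. The use of 80 in the next sentence, and adverse event forms tied to treatment cycles (Section 14.4c), fit that reading. It is plausible, but it does not remove the problem: the rule as written covers undosed patients, and data on them are collected.

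A third reply is that 80 is not a mistake. This also stands. A reader might take the gap between 80 and 88 as a wrong figure, but the bounds hold at both numbers.

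Finally, the effect is small beside the plan's own precision: at most 4.5 points at a true 50%, against a half-width of about 11 points. Section 11.2 attaches no stopping boundary, test or go/no-go rule to toxicity rates. Dose modification and expedited reporting act on individual patients, whatever the denominator. That limits the weight of the point but is no reason to keep the wording.

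**Conclusion.** The concern holds in conditional form and is minor. Sections 1.2c and 11.2 define the toxicity population as everyone enrolled, which as written includes any registered patient never given rucaparib. If there are such patients, rates are multiplied by dosed/enrolled.

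With an assumed 0 to 8 undosed of 88, that factor lies between 1.00 and 0.91. The lower end is a limiting case under the plan's allowance, and the realistic effect is probably smaller because the allowance also covers dosed but ineligible patients. The range rests on that allowance. It is not a forecast, and more undosed patients than planned would widen it.

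The stated precision and detection figures are right, and no decision rule in the plan depends on the toxicity rates.

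**What to change.** In Sections 1.2c and 11.2, use the same definition: toxicity is evaluated among all patients who took one or more doses of rucaparib, whether or not they are later found ineligible, with the two cohorts combined. Keeping dosed but ineligible patients matches what the present wording already does; the only change is to leave out undosed patients.

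In Section 11.2, add that 80 is the minimum planned size of this set if both cohorts reach their accrual goal. The 11% and 98% figures can stay as they are.

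The cost is one phrase in each section and a short note. No new data, patients, procedures or calculations are needed, and no efficacy analysis changes. Reporting the number registered but never dosed alongside the toxicity tables would let readers see the difference between the two populations.

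### Section 11.2 gives two non-equivalent criteria for ruling out a 3-month median PFS, the Brookmeyer-Crowley test and a 4.6-month cut, and does not say which governs

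*Combined protocol and SAP*

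**What the plan says.** Everything at issue is in Section 11.2 (Analysis Plan), in the part on investigator-assessed PFS.

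- Timing: "Analysis of IA-PFS will take place when 31 IA-PFS events/cohort have been observed" (with 40 evaluable patients per cohort).
- Power: "this design has 87% power to rule out a mPFS of 3 months or less", for a true median of 6 months, "at the 0.05 1-sided level".
- Basis: "Brookmeyer-Crowley test of null of 3 month mPFS versus alternative of 6 month mPFS", "with 10 months of accrual and 6 months" of follow-up.
- Decision sentence: "The observation of an mPFS of at least 4.6 months would be considered evidence to rule out an mPFS of 3 months or less".

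The same section has medians estimated by Kaplan-Meier with Brookmeyer-Crowley confidence intervals. It contains one further PFS criterion: if the response rate is below 25% but the median is at least 4.5 months, this may be taken as enough to go on to Phase III. No sentence ranks the test against the 4.6-month cut, gives the level or power of the cut, or says how the Kaplan-Meier median is read when the curve sits at exactly 50%.

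**The concern.** A Brookmeyer-Crowley test of a 3-month median asks whether the Kaplan-Meier estimate at 3 months is significantly above 50%. Equivalently, it asks whether the lower one-sided limit for the median lies above 3 months. The 4.6-month rule asks whether about half the patients are still progression-free at 4.6 months. These are different points on the curve, and a result on one side of one boundary need not be on the same side of the other.

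The report will show both a Brookmeyer-Crowley limit and an observed median. If they conflict, the plan supports either conclusion on what it calls a key secondary objective, and the choice would be made after the data are seen. The printed level and power also stand beside the cut, although they were derived for the test.

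**Working it through.** **Inputs, all from Section 11.2:** 40 patients per cohort; one-sided level 0.05; null median 3 months, alternative 6 months; 10 months' accrual plus 6 months' follow-up, so nobody is censored before 4.6 months on that basis; cut at 4.6 months. **Assumption, not in the plan:** exponential PFS, S(t) = 2^(-t/median), with event times seen continuously.

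**1. The plan's 87%.** S(3) is 0.5 under the null and 2^(-3/6) = 0.7071 under the alternative.
- Boundary: 0.5 + 1.645 × sqrt(0.25/40) = 0.630.
- Standard error under the alternative: sqrt(0.7071 × 0.2929/40) = 0.0720.
- Power: Φ((0.7071 - 0.6300)/0.0720) = Φ(1.071) = 85.8%.

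The log-log scale gives 86.1%, and a logit version using only the null standard error gives 87.3%. The printed 87% is therefore within about 2 points of a normal approximation to the named test. Under the exponential assumption the boundary of 0.630 corresponds to a median of 3 × ln 2/(-ln 0.630) = 4.50 months. The plan does not derive 4.6. One formula that gives it is 3 × exp(1.645/(ln 2 × sqrt(31))) = 4.59; that this is its source is an inference.

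**2. What the test attains.** z = (S - 0.5)/sqrt(S(1 - S)/40).
- 25/40 progression-free at 3 months: z = 1.63, not rejected.
- 26/40: z = 1.99, rejected.
- Level: P(X ≥ 26 | 40, 0.5) = 4.0%.
- Power: P(X ≥ 26 | 40, 0.7071) = 83.4%.

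**3. What the cut attains.** S(4.6) = 2^(-4.6/3) = 0.3455 under the null and 2^(-4.6/6) = 0.5878 under the alternative. The result depends on whether exactly 20/40 at 4.6 months counts as a pass.

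| Reading of the median | Level | Power |
|---|---|---|
| 21/40 needed (first time S ≤ 0.5) | 1.5% | 83.3% |
| Midpoint when S = 0.5 (simulated) | 1.8-2.3% | 87.3-87.6% |
| 20/40 suffices | 3.2% | 90.0% |

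**4. Conflict on the same data** (40 patients, no earlier censoring).
- 26/40 at 3 months and 18/40 at 4.6 months: passes the test, fails the cut.
- 25/40 at 3 months and 22/40 at 4.6 months: fails the test, passes the cut.

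**5. How often.** The number progression-free at 3 months is binomial(40, S(3)). Given that number, x, the number still progression-free at 4.6 months is binomial(x, S(4.6)/S(3)). Summing over the discordant cells:

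| True median | Disagree, 21/40 needed | Disagree, 20/40 suffices |
|---|---|---|
| 6 months | 13.3% (6.7% test only, 6.6% cut only) | 12.7% |
| 4.5 months | 22.4% | 23.2% |

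Simulation with the midpoint median gives 12-13% and 21-22%. Simulating the analysis at the 31st event, when some patients may be censored early, leaves the picture unchanged: test 4.2% and 83.8%; cut 1.5-1.8% and 83.8-87.3%.

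**6. Scan grid.** Sections 7.1 and 9.1 call for scans every 6 weeks in the first year: 42/30.4375 = 1.38 months, so scans at 1.38, 2.76, 4.14 and 5.52 months. If progression is seen only at scans, the 3-month estimate reflects the week-12 scan and the 4.6-month estimate the week-18 scan.
- For a latent 3-month median, S(2.76) = 0.5285 and S(4.14) = 0.3843. The level is 8.3% for the test. For the cut it is 4.9% (21/40 needed) or 9.1% (20/40 suffices).
- For a latent 6-month median, S(2.76) = 0.7270 and the test has power of about 90%.

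**The case against.** The best defence is that 4.6 months is only the usual translation of the test's rejection boundary into an observed median. The decision sentence follows directly after the test, 4.50 from step 1 is close to 4.6, and Section 11.2 already specifies Brookmeyer-Crowley limits. On that reading the test governs. It may well be what was meant, but the sentence calls the cut itself evidence, does not say it is approximate, and gives it no subordinate place.

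Three stronger readings are tempting, and the documents do not support them.

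- *The 0.05 and the 87% belong to neither rule.* The plan attributes both to the Brookmeyer-Crowley test. The 0.05 is that test's nominal level, with 4.0% the result of discrete counts, and 87% is near its normal approximation. The cut also has about 87% power with a midpoint median. Only the pair, taken together, is not attained by either rule in continuous time.
- *The rules would agree if PFS were exponential.* The disagreement rates above were computed under an exponential curve. That assumption maps one critical value roughly onto the other; it does not make the decisions the same.
- *The conflict decides whether a cohort goes to Phase III.* That route has its own 4.5-month criterion, worded permissively, and uses neither the test nor the 4.6-month cut.

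It is also fair to object that the continuous-time figures are not what 6-weekly scanning would deliver. On the scan grid the test's level rises to about 8%, and one reading of the cut gives 4.9%. An attained level of 4.0% must therefore not be printed without its conditions.

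**Conclusion.** The point holds as an ambiguity with a measurable consequence. Section 11.2 has two criteria for ruling out a 3-month median and names neither as governing. Under exponential, continuous-time PFS with 40 patients they give opposite answers in about 13% of trials at a true 6-month median and about 22-23% at 4.5 months, and this hardly depends on how the median is read.

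Under the same assumptions the printed 0.05 does not describe the cut (1.5-3.2%), and the test's attained power is 83.4% rather than 87%. The shortfall is modest and comes from approximation and discreteness rather than from a wrong test. The figures ignore the interim futility stop and shift under scan-based detection. What is at stake is the reported conclusion on a key secondary objective, not the primary analysis.

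**What to change.** In Section 11.2, name one governing rule. Suggested wording: *A median IA-PFS of 3 months or less is ruled out if the lower one-sided 95% Brookmeyer-Crowley confidence limit for the median exceeds 3 months. An observed median of about 4.6 months is an approximate guide to this boundary and is not itself a criterion.*

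Then:

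- restate the power as about 83%, with an attained level of about 4%, under exponential PFS and continuous event times;
- add that reading progression only at 6-weekly scans changes this, for a latent 3-month median, to a level of about 8% for the test (power about 90% at a latent 6-month median) and about 5-9% for the cut;
- say how the Kaplan-Meier median is read when the estimate equals exactly 50%.

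Section 11.1 already prints exact power and type I error for the response rate beside the nominal figures, so this follows the plan's own practice. The cost is wording and a stated power about 4 points less favourable (87% to 83%). No patients or data are added, and the separate 4.5-month Phase III criterion is unchanged.
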